slipping of the knife off the lesion. The incision should be deep enough such that it penetrates the mucosa and submucosa. A conventional biopsy forceps (Radial Jaw4, Boston Scientific, Natick, Mass) is then deeply introduced through the hole, and 2 bites are obtained per pass. A total of 4 passes will be performed, by passing the biopsy forceps through the incision on each occasion. The mucosal incision will then be closed with endoclips whenever possible. If the endoscopist at the time is concerned about inadequate tissue acquisition and plans to perform a subsequent intervention (i.e. EUS-CNB, EUS-FNA) then the endoclips will be placed after the EUS. Biopsies will be placed in formalin bottles and sent for histopathology. In case of technical failure, the endoscopist is permitted to choose another method to obtain biopsies (e.g. EUS-CNB, EUS-FNA...)

Pathologic evaluation

Specimens will be placed in buffered formalin and processed as normal forceps biopsy specimens; however, special care will be taken not to lose tiny specimen fragments. The pathologists will be blinded to the type of technique used, but all other information about the clinical history and site biopsied will be given. A positive diagnosis of a specific malignancy or of a specific benign disease by either technique will be accepted as a true positive. A histological diagnosis of atypical cells or abnormal cells will be considered a negative result. For malignancy, an “accurate diagnosis” will be considered one in which a tissue diagnosis obtained is compatible with that seen by subsequent surgery, alternative biopsy by another needle or sites, or clinical follow up.

Final diagnosis and definition

In the absence of surgical resection, diagnostic histology obtained by either technique will be considered the gold standard. When diagnostic histology is not available, a definitive diagnosis is established on the basis of long-term follow-up, surgery, or further procedures with biopsy. The diagnostic accuracy will be defined as the ratio between the sum of true positive and true negative values divided by the total number of procedures done in either technique. As per the discretion of the pathologist, the specimens may be subjected to immunostaining and if performed, the contribution to the diagnostic yield will be noted.

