With the assumption that diagnostic yield of “EUS-CNB” is 70% and that of “SINK” is 95%, and considering $\alpha = 5\%$ and $1-\beta = 80\%$, the required sample size is 36 patients in each group (total of 72 patients).

We will account for 20% drop out rate, giving a total of 90 patients, 45 in each arm.

Statistical analyses

Categorical parameters including gender, location of lesion, technical success and diagnostic accuracy will be compared by χ^2 -test or Fisher’s exact test. To compare diagnostic accuracy between the two techniques, we will use McNemar’s test. Continuous variables including age, size of lesion, follow-up period, needle passes and adequacy of specimens will be compared by the Student’s *t*-test or Wilcoxon rank sum test. All statistical analyses will be performed using SPSS software (version 15.0; SPSS, Chicago, IL), with results considered significant at *P* values < 0.05 .

- d. Early stopping rules.

A data safety and monitoring board (DSMB) will be appointed comprised of interventional endoscopists, mainly of [name], [name], and [name]. The DSMB will be responsible for reviewing all major complications (perforation, hospitalization for > 48 hours, bleeding requiring transfusion, deaths etc). If any serious adverse event is noted during the study then the DSMB will be required to meet. Additionally. The DSMB will perform a blinded analysis after enrolment and initial outpatient follow-up of 50% of the study cohort.

Interim analysis will be performed at 50% recruitment. If a $> 20\%$ difference in sensitivity is found between both methods then the study will be terminated early.

8. Risks

- a. Medical risks, listing all procedures, their major and minor risks and expected frequency.

This study is classified as greater than minimal risk and potential complications related to EUS-CNB or SINK procedure are following:

- 1) The needle puncture may cause inflammation or scarring of the lining of the digestive tract which may cause abdominal pain and ulceration.
- 2) Perforation: Only physicians specially trained in EUS will be performing these procedures. Patients will be kept a minimum of 2 hours after the procedure is completed, during which time any perforation would be clinically recognized.

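### The scoring rules for a positive reading conflict: any specific diagnosis is a true positive without condition, yet resection, where done, is implied to be the reference, and nothing says which prevails

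*Combined protocol and SAP*

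**What the plan says.** The primary outcome (section 2 and section 7a) is diagnostic accuracy, SINK against EUS-CNB. Section 4, under Final diagnosis and definition, defines it as "the ratio between the sum of true positive and true negative values divided by the total number of procedures done in either technique". Who counts as a true positive therefore largely decides the result.

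Three sentences bear on a positive reading:

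1. Section 4, Pathologic evaluation: "A positive diagnosis of a specific malignancy or of a specific benign disease by either technique will be accepted as a true positive". No confirmation is asked for.
2. Same subsection, for malignancy only. An accurate diagnosis is one where "a tissue diagnosis obtained is compatible with that seen by subsequent surgery, alternative biopsy by another needle or sites, or clinical follow up".
3. Section 4, Final diagnosis and definition: "In the absence of surgical resection, diagnostic histology obtained by either technique will be considered the gold standard". Where there is no diagnostic histology, "a definitive diagnosis is established on the basis of long-term follow-up, surgery, or further procedures with biopsy".

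On negative readings the plan says "A histological diagnosis of atypical cells or abnormal cells will be considered a negative result". It does not define a true negative or a false positive.

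The planning rates of 95% and 70% are called diagnostic accuracy in section 7a. Section 7c introduces the same two figures with "With the assumption that diagnostic yield of".

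**The concern.** Sentence 1 settles the score when the pathology report is issued. Sentences 2 and 3 let later evidence settle it. They part company for a specific biopsy diagnosis that resection then shows to be wrong, whether benign on biopsy and something else at surgery or the reverse.

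If sentence 1 governs, such a patient is a success. The false-positive class is then empty by definition, and what is called accuracy becomes the proportion of procedures with a specific diagnosis, plus any true negatives. A technique that returned confident but wrong diagnoses would lose nothing on the primary endpoint. That outcome would also largely duplicate the first secondary objective, diagnostic histological tissue acquisition.

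If the other sentences govern, the patient is an error. Two analysts could each follow section 4 faithfully and report different primary results from the same data, and the choice could be made after the data are seen.

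**Working it through.** **Setting the sentences side by side**

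| Patient with a specific index diagnosis | Sentence 1 | Sentence 2 (malignancy) | Sentence 3 (reference) |
|---|---|---|---|
| Resection agrees | success | accurate | correct |
| Malignant reading, resection contradicts | success | not accurate | wrong (implied) |
| Benign reading, resection contradicts | success | does not apply | wrong (implied) |
| No resection, no contrary evidence | success | no score stated if nothing later is available | correct |

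The second and third rows are the conflict. It is explicit for malignancy. For benign disease it follows from the opening condition of sentence 3.

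**Reproducing the planned size.** Inputs from section 7c: 95% and 70%, alpha 5% (two-sided assumed, since the sidedness is not stated), power 80%. Mean rate = (0.95 + 0.70)/2 = 0.825.

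n per arm = [1.96 × √(2 × 0.825 × 0.175) + 0.8416 × √(0.70 × 0.30 + 0.95 × 0.05)]² / 0.25² = (1.053 + 0.427)² / 0.0625 = 35.1, rounded up to 36.

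The total is 72, and 72/0.80 = 90. The plan's figures reproduce and are not in question.

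**Illustration 1: power.** Assumptions: 95% and 70% are rates of specific diagnosis, and 5% of these are contradicted in each arm and scored as errors. The documents give no such rate. The success rates become 0.95 × 0.95 = 90.25% and 0.70 × 0.95 = 66.5%. Power is by exact enumeration of the binomial outcomes, 36 per arm, two-sided 5%. The tests are unpaired, because each patient is randomised to one technique.

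| Success rates | Chi-square | Fisher |
|---|---|---|
| 95% vs 70% | 85% | 76% |
| 90.25% vs 66.5% | 71% | 61% |

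The sample-size formula above, applied to 90.25% and 66.5%, gives 46 per arm. If no reading is contradicted, sentences 1 and 3 agree and nothing changes.

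**Illustration 2: the P value.** Start near the planned rates: 34/36 (94%) against 25/36 (69%), Fisher p = 0.012. Score contradicted readings as errors:

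| Contradicted, SINK / CNB | Successes of 36 | Fisher p |
|---|---|---|
| 1 / 0 | 33 vs 25 | 0.035 |
| 1 / 1 | 33 vs 24 | 0.018 |
| 2 / 1 | 32 vs 24 | 0.045 |
| 2 / 2 | 32 vs 23 | 0.025 |
| 0 / 2 | 34 vs 23 | 0.003 |
| 2 / 0 | 32 vs 25 | 0.079 |

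Only the last case passes 0.05. There the uncorrected chi-square test gives p = 0.042, and section 7c allows either test.

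**The case against.** The strongest reply is that the text has a coherent reading. A specific diagnosis is accepted by default, resection overrides it where done, and a malignant diagnosis must also fit later evidence. On that reading the term true positive is defined once, the second sentence defines a different term (an accurate diagnosis, for malignancy), and the third sets the reference standard under its own heading. Surgery as the reference is implied, not stated. All of this is fair. What it does not supply is a sentence saying that the first rule is provisional, and that rule is worded as final. A reader who applies it as written scores a disproved diagnosis as a success.

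Stronger readings are tempting, and the documents do not support them:

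- A reader might infer that a malignant diagnosis without later surgery or biopsy must be scored inaccurate, lowering both arms substantially. But section 4 also accepts clinical follow-up, asks only for compatibility, and never says that an unconfirmed malignancy is an error. Follow-up is left to clinical indication, so evidence may be patchy, but that is a different complaint. No power loss is claimed on this ground.
- A reader might infer that the choice of rule takes the primary result across 0.05. Among the cases worked, this happens only with two contradicted SINK readings, none for CNB, and Fisher's test.
- A reader might take the word yield in section 7c as evidence that the literal first rule was intended. Section 7a calls the same figures accuracy, and the cited 92.8% for SINK is called accuracy in the abstract and yield in the background. The terms are used interchangeably, so neither is evidence for a rule.

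**Conclusion.** The point holds for positive readings that later evidence contradicts. Section 4 scores them as successes by one sentence and as errors by others, without saying which governs. Taken literally, its first sentence stops a wrong specific diagnosis from ever lowering the primary outcome. This is more than missing detail, because a stated rule, followed as written, gives the wrong score.

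The size is unknown. It depends on how many patients are resected or otherwise re-examined and how often the index diagnosis is overturned, and the documents give neither. Illustration 1 shows a loss of about 14 to 15 percentage points of power at an assumed 5% in both arms, provided that 95% and 70% are yields. Illustration 2 shows that the primary result could cross 0.05, not that it will. The change should be made, since it concerns the numerator of the primary endpoint and is cheap.

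**What to change.** Replace the unconditional acceptance in Pathologic evaluation with one rule for both arms and for benign and malignant diagnoses:

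- A specific index diagnosis counts as correct unless it is contradicted by surgical histology, a later specific biopsy diagnosis or documented clinical follow-up.
- If contradicted, it counts as incorrect and stays in the denominator.
- With no later evidence, it counts as correct.

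Align the malignancy sentence with this rule. Report the proportion with a specific diagnosis, unverified, separately as yield, so that yield and accuracy are distinct quantities. Use one term for the 95% and 70% in sections 7a and 7c.

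The cost is protocol wording only, and no extra patients or procedures are proposed. The downside is that accuracy, and power at the planned size, may be lower than under the literal first sentence, by an amount that depends on the unknown contradiction rate.

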Linear EUS will be used with color and pulsed Doppler to scan the area for vessels. The accessory channel is used to pass through devices for tissue sampling. The lesion will be sampled with a 22-gauge Procore needle (ProCore, Cook Medical Inc., Winston-Salem, NC) using the slow capillary suction technique with 5 to 15 to-and-fro movements with each pass. The slow capillary suction technique and fanning techniques will be used with each pass. The slow capillary suction technique involves the assistant simultaneously pulling out the stylet slowly and continuously over approximately 20s while the stylet is simultaneously removed up to 2/3 of its entire length. The fanning technique will be used. This technique involves positioning the needle at 3 different areas within the mass and then moving it back and forth 5 times in each area to procure tissue (3×5). The needle will be positioned at different areas within the mass by using the “up-down” dial of the echoendoscope and with minimal use of the elevator to avoid needle dysfunction. A total of 4 passes will be performed and then the procedure terminated. No cytopathologist will be present to review the specimens. All specimens will be placed in formalin bottles and sent for histopathology. If the samples are of insufficient quality such that a histological diagnosis would not likely be obtained after a total of 4 passes as per the impression of the endoscopist, he/she will be permitted to perform an alternative method; such as, SINK, EUS-FNA, EUS-CNB etc...

Definitions:

Technical Failure: Inability to complete the 4 assigned passes as determined by randomization. Malfunction of the needle before 4 needle passes is an example.

Adverse events: Refer to Tables 1 and 2. [12]

Operation Time: Time from the beginning of the incision or needle insertion, to completion of tissue acquisition per protocol.

Patients receiving the EUS-SINK technique:

A conventional needle-knife sphincterotome (Microknife XL; Boston Scientific Inc, Natick, Mass) connected to an electrosurgical unit (ICC 200; ERBE Electromedizin, Tübingen, Germany) will be utilized. The setting used would be ENDOCUT I, Effect 3, Duration 2 and Interval 1. Under direct endoscopic vision, a 6 to 12-mm linear incision is made from the periphery of the lesion to the highest convexity zone of the lesion. This direction of cut is important as it will help avoid unnecessary extension of the incision outside the lesion from

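### The primary endpoint formula counts undefined true negatives that only non-diagnostic samples could supply, and for unresected benign diagnoses it measures yield, not verified accuracy

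*Combined protocol and SAP*

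**What the plan says.** Section 2 makes diagnostic accuracy the primary outcome. Section 4, under Final diagnosis and definition, computes it as "the ratio between the sum of true positive and true negative values divided by the total number of procedures done in either technique".

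The terms of that ratio are treated as follows.

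- **True positive** (Pathologic evaluation): "A positive diagnosis of a specific malignancy or of a specific benign disease by either technique will be accepted as a true positive".
- **Negative** (same section): "A histological diagnosis of atypical cells or abnormal cells will be considered a negative result". The words true negative occur only in the ratio.
- **Reference standard** (Final diagnosis and definition): "In the absence of surgical resection, diagnostic histology obtained by either technique will be considered the gold standard". Otherwise, "When diagnostic histology is not available, a definitive diagnosis is established on the basis of long-term follow-up, surgery, or further procedures with biopsy".
- **Malignancy only** (Pathologic evaluation): an accurate diagnosis is one where "a tissue diagnosis obtained is compatible with that seen by subsequent surgery, alternative biopsy by another needle or sites, or clinical follow up".

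Section 4e classes an inconclusive pathology report as an inadequate sample, under failure of the initial method. What follows is discretionary: repeat sampling, surgery or surveillance at 6-12 months. The study calendar ends with the telephone call at one week and leaves longer follow-up to clinical indication. Section 4f requires none.

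The planning rates of 95% and 70% are called accuracy in Section 7a and yield in Section 7c. The early-termination rule in Section 7d uses sensitivity.

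**The concern.** An accuracy ratio needs a group in which the correct answer is negative. This trial has none, so the true-negative term has no evident content. If an analyst fills it with atypical or inconclusive samples that later follow-up appears to support, failures to obtain a diagnosis become successes. More of that credit goes to the arm with more failures: 30% for EUS-CNB against 5% for SINK at the planned rates. The pathologist reads specimens blind ("The pathologists will be blinded to the type of technique used"), but nothing says who would assign a true negative or from what evidence.

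The reference standard raises a second problem. When a specific benign diagnosis is not followed by resection, the same histology is both test and reference. A wrong diagnosis there cannot be scored as wrong, so a yield result would be reported as accuracy.

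**Working it through.** **1. What could be a true negative?**

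- A patient without a lesion: none, because eligibility (Section 5) requires a subepithelial tumour of at least 15 mm.
- A specific benign diagnosis, read as negative for malignancy: no, because it is already a true positive.
- What remains is atypical, abnormal or inconclusive histology, or no usable specimen. Atypical and abnormal cells are called a negative result. Section 4e calls an inconclusive report a failure. No sentence scores either as a true negative, and none excludes it.

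**2. What can be scored as wrong?**

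| Assigned-technique result | Later evidence | Scoring under the text |
|---|---|---|
| Specific benign | No resection | Own gold standard; cannot be wrong |
| Specific benign | Resection | The reference sentence implies that resection governs, but the true-positive sentence has no exception |
| Specific malignant | Any | True positive by one sentence; accurate only if compatible by another |
| Non-diagnostic | Discretionary | Negative; whether true or false is not stated |

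**3. The plan's own sample size.** Inputs from Section 7c: 70% v 95%, alpha 5%, power 80%. Sidedness is not stated; two-sided is assumed. With the pooled formula and no continuity correction, the mean proportion is 0.825 and

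n = [1.960 × √(2 × 0.825 × 0.175) + 0.842 × √(0.70 × 0.30 + 0.95 × 0.05)]² / 0.25²
= (1.053 + 0.427)² / 0.0625 = 35.06, so **36 per arm**.

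Allowing 20% drop-out gives 36 / 0.8 = **45 per arm**, 90 in total. Both match the plan.

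**4. Illustration of true-negative credit.** Let q be the share of non-diagnostic samples credited, equal in both arms. The documents give no value. Read 95% and 70% as true-positive-only rates. The endpoint is then

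rate = yield + q × (1 − yield), and the difference = 25 × (1 − q) points.

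Power is the exact binomial probability that a two-sided unpaired test gives p < 0.05 with 36 per arm.

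| q | EUS-CNB | SINK | Difference (points) | Chi-square power | Fisher power |
|---|---|---|---|---|---|
| 0 | 70.0% | 95.0% | 25.0 | 85% | 76% |
| 0.10 | 73.0% | 95.5% | 22.5 | 81% | 68% |
| 0.25 | 77.5% | 96.25% | 18.75 | 72% | 54% |
| 0.50 | 85.0% | 97.5% | 12.5 | 52% | 26% |

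The Fisher figure is below 80% even at q = 0, so part of each Fisher shortfall comes from the choice of test. The chi-square column is the cleaner measure of the effect of crediting. Its 85% at q = 0 is exact; the approximate formula in step 3 gives 81%.

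**5. Illustration of self-reference.** Suppose a share e of specific diagnoses is wrong and none is verified, which gives an upper bound on the effect. The true difference is 95 × (1 − e in SINK) − 70 × (1 − e in EUS-CNB).

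- 5% wrong in both arms: 90.25 − 66.5 = 23.75 points.
- 10% wrong in both arms: 85.5 − 63.0 = 22.5 points.
- 10% wrong in SINK only: 85.5 − 70 = 15.5 points.
- 10% wrong in EUS-CNB only: 95 − 63 = 32 points.

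All four would be scored as 25 points. The error rates are assumptions.

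**The case against.** The strongest reply is that the true-negative term is an empty textbook phrase. Atypical cells are called negative, Section 4e treats inconclusive reports as failures, and no sentence credits them. The protocol also uses accuracy and yield interchangeably: the 92.8% published for SINK in 14 patients is accuracy in Section 1 and yield in Section 3. On that reading, and leaving the malignancy rule aside, the endpoint is yield and the planned power stands.

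Much of this stands. The interchangeable wording favours reading 95%/70% as true-positive-only rates, and nothing shows that anyone intends to credit failures. If the planning rates did already include true negatives, planned power would be unaffected as well. But an empty term should not be in the formula for the primary endpoint, and a result computed that way is yield under the name of accuracy.

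It can also be said that the reference standard is disclosed, that resection appears to override it, and that equal error rates barely move the difference. That is fair. The larger shifts in step 5 need error rates that differ by arm, and the documents give no evidence of such a difference.

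The comparison above uses unpaired tests because patients are randomised to one technique. Section 7c names McNemar's test for accuracy; that is a separate matter, not settled here.

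**Conclusion.** The point holds as a fault in the stated endpoint rule. Read literally, the formula either credits non-diagnostic samples as successes or reports yield as accuracy. The conflict over malignancy leaves a further group of patients without a settled score.

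A reader might infer three stronger things that the documents do not support.

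- *That the trial will lose power.* The loss depends on a crediting share that the protocol does not give, and on 95%/70% being true-positive-only rates. The fall from 85% to 52% is an illustration over q = 0 to 0.50, not a forecast.
- *That the whole endpoint is circular.* The self-reference is clear only for unresected specific benign diagnoses. Malignancy has a compatibility rule, and resection appears to govern where it is done.
- *That the sample size is wrong.* It reproduces.

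Confidence is high that the definition is missing, and lower about its numerical consequences. It should be fixed before outcomes are compared by arm.

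**What to change.** Amend Section 4 and carry the change through.

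1. Delete the true-negative term.
2. Count each patient once, under the assigned technique. A success is a specific histological diagnosis from that technique's specimens that is not contradicted by resection, or by the malignancy check, where such evidence is available.
3. Count every atypical, inconclusive or absent specimen as a failure, whatever follow-up or a rescue method later shows. A technical failure ("Inability to complete the 4 assigned passes as determined by randomization") that leaves no diagnosis is a failure too.
4. Reconcile the blanket true-positive sentence with the malignancy compatibility sentence, so that one rule scores malignant diagnoses.
5. Call the endpoint diagnostic yield, or keep accuracy and state that it is unverified without resection. Use the one term in the hypothesis, sample size and interim rule, and say how it differs from secondary outcome 1 (diagnostic histological tissue acquisition).
6. As a secondary analysis, report by arm the number of diagnoses checked against resection or a later biopsy, and their concordance.

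**Cost.** A protocol amendment, with no new visits or procedures. The 36 evaluable and 45 randomised per arm still stand if 95% and 70% are taken as success rates under this definition. The claim becomes narrower than accuracy. Because not everyone has a resection, errors remain detectable only in the verified subset. Keeping a full accuracy claim would need an independent reference for every patient, and so follow-up that the protocol does not schedule.

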Thus, this study will provide essential data on two techniques to help decipher which is the optimal method of tissue acquisition.

We hypothesize that the SINK technique will have a higher diagnostic accuracy than EUS-CNB for the diagnosis of UGI SETs.

4. Study Procedures

- Study design, including the sequence and timing of study procedures (distinguish research procedures from those that are part of routine care).

This is a prospective, randomized study. All procedures are part of routine care and not experimental. All patients will begin their endoscopy with a standard gastroscope followed by electronic radial/linear scanning video echoendoscope prior to randomization to ascertain the wall layer of origin for the tumor. This EUS exam will be performed under the same anesthetic as the study intervention. Patients will be consented prior to endoscopy.

Patients who are candidates for this study (see inclusion criteria) will be randomized as to receive either EUS-CNB or SINK technique (computer generated randomization sequence, sealed envelopes). The endoscopist will not be blinded to the type of technique used however the study pathologist will be blinded.

Patients receiving the EUS-CNB technique:

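### Primary accuracy is counted per procedure and assigned a paired test, although rescue with the other technique is allowed; the plan should fix one assigned-procedure result per patient and one unpaired test

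*Combined protocol and SAP*

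**What the plan says.** The only definition of the primary measure is in section 4, under Final diagnosis and definition. It is a ratio of true results "divided by the total number of procedures done in either technique". The unit is the procedure, and nothing ties it to the assigned or first procedure.

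Rescue is permitted in both arms. In the core needle biopsy (CNB) arm, if the endoscopist judges the samples insufficient after four passes, "he/she will be permitted to perform an alternative method; such as, SINK, EUS-FNA, EUS-CNB etc". In the SINK arm, after technical failure, "the endoscopist is permitted to choose another method to obtain biopsies". Section 4e allows cross-over between the two techniques, in the same session or later, and also allows EUS-FNA, surgery or surveillance.

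The definition of technical failure, by contrast, is tied to allocation: "Inability to complete the 4 assigned passes as determined by randomization".

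Section 7c lists diagnostic accuracy among the variables to be compared by chi-square or Fisher's test. Its next sentence assigns the comparison of accuracy between techniques to McNemar's test. No analysis set is named.

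**The concern.** Two parts of the primary analysis do not fit a parallel-group trial.

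- **Denominator.** A patient assigned to CNB and rescued with SINK contributes a failed procedure to CNB and a second procedure to SINK. The second is done on a lesion selected because the first attempt failed. The two rates then share patients, and the SINK rate includes lesions that were not randomised to it. Whether to rescue, and by which method, is left to the unblinded endoscopist, so under the literal reading that discretion moves the primary rates.
- **Test.** McNemar's test compares two results on the same patient. Here the only patients with both would be those who crossed over, and they are selected for failure of the first technique.

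The same data could therefore give different primary results, with the choice still open when the data are seen.

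**Working it through.** **1. The plan's own figure.** Inputs from section 7c: 70% and 95%, alpha 5%, power 80%. With two independent proportions, two-sided, pooled variance and no continuity correction (mean proportion 0.825):

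n = [1.960 × √(2 × 0.825 × 0.175) + 0.842 × √(0.70 × 0.30 + 0.95 × 0.05)]² / 0.25² = (1.053 + 0.427)² / 0.0625 = 35.06, rounded up to 36 per group.

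Then 72 / 0.8 = 90. Both stated figures reproduce, from a formula that takes one result per patient in two independent arms.

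**2. Power with one assigned result per patient (exact, two-sided 5%, 70% vs 95%).**

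| Test | Evaluable per arm | Power |
|---|---|---|
| Chi-square, uncorrected | 36 | 85.1% |
| Fisher | 36 | 75.9% |
| Fisher | 38 | 79.2% |
| Fisher | 39 | 80.7% |
| Fisher | 40 | 82.1% |

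**3. Literal reading, cross-over counted.** Let f be the share of first-technique failures rescued with the other study technique, and x and y the rescue yields of SINK and CNB. The documents give none of these. I assume x from 50% to 75% and y from 12.5% to 40%. (The only 12.5% in the documents is an EUS-FNA result, so the lower CNB yield is a bare assumption.)

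- SINK rate = (0.95 + 0.30 f x) / (1 + 0.30 f)
- CNB rate = (0.70 + 0.05 f y) / (1 + 0.05 f)
- Patients counted twice = 36 × (0.30 + 0.05) × f

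Example, f = 0.25, x = 0.5, y = 0.4: SINK = 0.9875 / 1.075 = 91.9%; CNB = 0.705 / 1.0125 = 69.6%; difference 22.2 points.

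| f | Counted twice | Difference (points) | Simulated power, chi-square |
|---|---|---|---|
| 10% | 1.3 | 23.8 to 24.7 | 81 to 84% |
| 25% | 3.2 | 22.2 to 24.3 | 75 to 84% |
| 50% | 6.3 | 19.9 to 23.8 | 63 to 83% |
| 100% | 12.6 | 16.0 to 23.1 | 39 to 82% |

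The last row is extreme, because EUS-FNA, surgery and surveillance are also allowed and enter neither rate. If rescue is as accurate as first use (x = 0.95, y = 0.70), the difference is 25 points at every f.

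**4. Repeat CNB counted instead.** With share g of CNB failures, CNB rate = (0.70 + 0.30 g y) / (1 + 0.30 g). Set against 95%, the difference is 25.9 to 26.7 points at g = 10%, 27.1 to 29.0 at 25% and 28.9 to 32.5 at 50%.

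**5. Both counted, with g = f.** CNB rate = (0.70 + 0.05 f y + 0.30 f y) / (1 + 0.35 f), with SINK as in step 3. The difference is 24.7 to 26.4 points at 10% and 24.3 to 28.2 at 25%. The two mechanisms partly offset.

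**The case against.** The strongest reply is that context already settles the meaning. The CNB instructions say "A total of 4 passes will be performed and then the procedure terminated". Section 4e sits under a treatment-failure heading and separates the first method from any other. Section 4f says the protocol requires nothing further after the diagnostic procedure, which makes a later rescue hard to read as a study procedure. Further biopsies have another role, as reference: "alternative biopsy by another needle or sites, or clinical follow up", and, where diagnostic histology is lacking, "a definitive diagnosis is established on the basis of long-term follow-up, surgery, or further procedures with biopsy". The sample size counts patients and reproduces from two independent proportions.

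Most of this stands: the intended reading is very probably one assigned procedure per patient. It does not repair the text. The definition still counts procedures, same-session rescue and repeat CNB remain open, and the technical-failure definition shows that the authors could tie a measure to allocation. The test is a separate defect: McNemar's test is wrong under the benign reading too.

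It is also fair to say that no bias is shown, since every rescue rate and yield is assumed. That stands in full.

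A reader might infer that the listed drop-outs would remove lesions, such as a lipoma, because of the assigned biopsy's histology. No text proposes this. The EUS examination takes place "prior to randomization to ascertain the wall layer of origin for the tumor", and the exclusion criteria treat lipomas and varices as lesions not needing tissue.

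**Conclusion.** The definition and the test should be corrected: as written, the plan can count a patient in both techniques and applies a paired test to unpaired arms. The stated 36 per group is sound and fits the assigned-procedure reading.

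Three stronger conclusions are tempting, and the documents do not support them.

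- **That the trial is biased in a known direction or has lost power.** Under the assumed inputs the difference may fall, stay at 25 points or rise. The low power figures come from cross-over alone at high rates. The effect is small if few failures cross over.
- **That the authors meant to count rescue procedures.** The context above points the other way.
- **That both techniques share one pooled denominator.** With no rescue that gives 0.70 × 36 / 72 = 35% and 0.95 × 36 / 72 = 47.5%, which cannot be squared with the planned 70% and 95%.

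**What to change.** - **Definition.** Primary accuracy is the number of patients whose assigned procedure's own specimens gave a correct result, divided by patients randomised to that arm less the drop-outs listed in section 5. Each patient gives one result, and drop-outs are reported by arm.
- **Technical failures.** Keep them in the denominator, scored on whatever assigned specimens were obtained, or as non-diagnostic if there were none.
- **Rescue specimens.** Use them only to establish the final diagnosis and in a descriptive table. The permission to rescue is untouched.
- **Test.** Delete McNemar's test for accuracy and name one unpaired test in advance. The uncorrected chi-square test matches the stated 36 per group. If Fisher's test is preferred, state that its power is 75.9% at 36 and that 80% needs about 39 to 40 evaluable per arm. That uses 3 to 4 of the 45 − 36 = 9 patients per arm allowed for drop-out.

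The cost is one rewritten definition, one analysis-set sentence and one deletion, with no change to the 90 planned. The downside is that rescue successes count towards neither technique's primary rate, and rescue specimens need separate labels. This change does not settle what counts as a true negative, which the definition also uses.
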